3.3. Primary endocrine therapy in premenopausal breast cancer patients

Limited data are available on neoadjuvant treatments administered in premenopausal patients. In a study focused on 13 premenopausal women with endocrine responsive disease, neoadjuvant therapy with a gonadotropin-releasing hormone (GnRH) analogue induced a 54% rate of clinical response after 3 months of treatment (21). Torrisi et al. analyzed the efficacy of letrozole in combination with GnRH analogues and revealed among its 32 evaluable patients a median duration of therapy of 5.2 months for letrozole. A single patient (3%) obtained a complete clinical response, which was confirmed as by pCR upon pathological examination, whereas 15 patients (47%) obtained a partial response that produced an overall response rate of 50%; no patients progressed during treatment (22).

The STAGE study randomized 204 premenopausal women with ER-positive, HER2-negative breast cancer to receive goserelin 3.6 mg/month plus either anastrozole and tamoxifen placebo or tamoxifen and anastrozole placebo for 24 weeks before surgery. More patients in the anastrozole group had a complete or partial response than did those in the tamoxifen group during the 24 weeks of neoadjuvant treatment (70.4% vs. 50.5%, respectively) (23).

3.4. GnRH agonist and GnRH antagonist

3.4.1. GnRH agonist

GnRH or LHRH (luteinizing hormone-releasing hormone agonist) analogues or agonists are synthetic peptide drugs modeled after the human hypothalamic gonadotropin-releasing hormone (GnRH). GnRH agonists are designed to interact with the GnRH receptor and modify the release of pituitary gonadotropins, follicle-stimulating hormone (FSH) and luteinizing hormone (LH), for therapeutic purposes. Upon administration of GnRH agonists an initial stimulating action of the hypophysis occurs – termed a «flare» effect - which eventually causes a paradoxical and sustained drop in gonadotropin secretion. This second effect was termed «downregulation» and can be observed after about 10 days. While this phase is reversible upon stopping the medication, it can be maintained when GnRH agonist use is continued for a prolonged period of time. For some patients, there can be a delay of approximately 2-4 months until downregulation of the gonadotropins occurs.

3.4.2. GnRH agonist and antagonist in prostate cancer

Degarelix (tradename: Firmagon), a new GnRH receptor blocker (antagonist), was developed as a novel therapy for patients with prostate cancer. Degarelix binds to and blocks the GnRH receptors in the anterior pituitary gland, resulting in decreased secretion of both LH and FSH. This leads directly to a rapid decrease in the production of testosterone. Testosterone suppression to castration levels (≤ 0.5 ng/mL) (24) is achieved within 1–3 days of administration.

In two phase II dose-finding clinical trials, a starting dose of 240 mg degarelix and maintenance doses of 160 mg or 80 mg were shown to effectively suppress testosterone levels in patients with prostate cancer, with no evidence of testosterone surge or inducement of clinical flare (25,26).

In a dose-finding study CS07, patients were allocated to one of eight single doses. These were: 120 mg (40 mg/mL); 120 mg (20 mg/mL); 160 mg (40 mg/mL); 200 mg (40 mg/mL); 200 mg (60 mg/mL); 240 mg (40 mg/mL); 240 mg (60 mg/mL); and 320 (60 mg/mL). The single 240 mg (40 mg/mL) dose was identical to the starting dose being proposed for registration. Based on the results for the primary and secondary endpoints relating to serum testosterone suppression, doses of 200 mg (40 mg/mL) and 240 mg (40 mg/mL) were the most efficacious as measured by response rates $\geq 95\%$. The study provides supportive evidence for the efficacy of the proposed initial dose of 240 mg (40 mg/mL) (27).

A pivotal study compared the efficacy and safety of two s.c. degarelix treatment regimens and an i.m. leuprolide (L) 7.5 mg treatment regimen administered every 28 days for up to 12 months in patients with prostate cancer. The two degarelix regimens were both initiated with a dose of 240 mg (40 mg/mL) followed 28 days later by a maintenance dose of either 160 mg (40 mg/mL) or 80 mg (20 mg/mL) repeated every 28 days. The results for the primary analysis showed that both D240/160 and D240/80 treatment regimens were effective in suppressing testosterone from Day 28 to Day 364. The results also showed that both D240/160 and D240/80 treatment regimens were non-inferior to L7.5 in suppressing testosterone from Day 28 to Day 364 (28).

A phase III study was conducted to compare the efficacy of monthly administrations of the luteinizing hormone releasing hormone agonists triptorelin and leuprolide to induce and maintain castrate levels of serum testosterone in men with advanced prostate cancer. Men with advanced prostate cancer were randomly assigned to receive triptorelin 3.75 mg or leuprolide 7.5 mg. In all, 284 men received either triptorelin (140) or leuprolide (144). The percentage of men with castrate levels of serum testosterone was lower at 29 days for triptorelin than for leuprolide (91.2% vs 99.3%; point estimate - 8.0, 95% confidence interval - 16.9% to - 1.4%), but equivalent at 57 days (97.7% vs 97.1%). The mean (98.8% vs 97.3%) and cumulative (96.2% vs 91.2%) castration maintenance rates between 29 and 253 days were equivalent between the treatment groups (29).

3.4.3. GnRH agonist and antagonist in breast cancer

Triptorelin administered at a dose of 3.75 mg was shown to induce strong estradiol suppression among premenopausal patients with breast cancer (30). Moreover, letrozole in combination with triptorelin at the dose of 3.75 mg q 28 days induces a more intense estrogen suppression than tamoxifen + triptorelin in premenopausal patients with early breast cancer. Prospectively collected hormonal data were available in a study that included 81 premenopausal women, of whom 30 were assigned to receive tamoxifen + triptorelin whereas 51 were assigned letrozole + triptorelin +/- zoledronate with a median age of 44 years for both groups of patients. Letrozole + triptorelin (+/- zoledronate) induced stronger suppression of median E2 serum levels ($P = .0008$), LH levels ($P = .0005$), and cortisol serum levels ($P < .0001$) compared with tamoxifen + triptorelin (31).

It therefore seems reasonable to compare the GnRH agonist triptorelin at the dose of 3.75 mg every 28 days with the GnRH antagonist degarelix at the initial dose of 240 mg s.c., followed by 80 mg s.c. on day 1 of subsequent 28 day cycles.

3.5. Plasma estradiol levels during endocrine therapy with AI

The guidelines of Smith et al. for the use of adjuvant AIs after chemotherapy-induced amenorrhea (32) recommend caution in the situation where estradiol levels determined by highly sensitive/specific methods such as GC-MS/MS are >10 pmol/L (>2.72 pg/mL) while on an AI, because this indicates that the AI is not exerting its full effectiveness. Thus optimal suppression will be defined as E2 levels ≤ 2.72 pg/mL or ≤ 10 pmol/L.

3.6. Rationale of the trial

Despite the advances achieved with primary therapy, novel treatment approaches are still necessary to increase disease control. Neoadjuvant endocrine therapy with a combination of GnRH agonist and AIs is effective for a select group of premenopausal patients.

Degarelix induces a fast and profound reduction in LH, FSH and in turn, testosterone suppression. Its activity in suppressing ovarian function of premenopausal women might therefore be faster than that of the GnRH agonists, and for some patients this might mean shortening time to ovarian suppression by several weeks. A difference in onset of action might have significant clinical value in patients who are candidates for short-term neoadjuvant endocrine treatment.

4. Trial objectives and endpoints

The primary objective is to compare the endocrine activity of neoadjuvant degarelix and triptorelin in premenopausal patients receiving letrozole for primary endocrine responsive breast cancer. The endocrine activity is measured by time to optimal ovarian function suppression.

4.1. Primary endpoint

Time to optimal ovarian function suppression: time from the first injection of degarelix or triptorelin to the first assessment of centrally assessed 17- β -estradiol (E2) level in the range of optimal ovarian function suppression (≤ 2.72 pg/mL or ≤ 10 pmol/L) during the 6 cycles of neoadjuvant treatments. Time for patients who do not reach the targeted E2 level will be censored at the last E2 assessment date.

[figure not shown]
4.2. Secondary endpoints

- Tolerability: adverse events according to CTCAE version 4
- Ki67 proliferation marker changes
- The Preoperative Endocrine Prognostic Index (PEPI) score determined after completion of neoadjuvant therapy or at the time of surgery
- Best overall (disease) response: defined as best response recorded from the start of treatment across all time points until disease progression. Confirmation of partial or complete response by an additional scan is not required in this trial. Best overall response will be determined by a team consisting of the study chair, co-chair and IBCSG Head of Medical Affairs. Tumor assessment will use WHO response criteria.
- Node-negative disease at surgery
- Breast-conserving surgery (BCS) rate
- Patient-reported symptoms (PRS) outcomes (see Section 16.5)

5. Trial design, duration and termination

5.1. Trial schema

Randomization allocation 1:1 to one of the two arms

5.2. Sample size and trial duration

- Neoadjuvant endocrine therapy of letrozole with either degarelix or triptorelin in 28 days cycle for a total of 6 cycles.
- Total of 50 patients (Arm A: 25 and Arm B: 25) will be enrolled.
- Estradiol (E2) levels will be determined centrally from samples taken at day 1 of first treatment cycle before the administration of the first dose (baseline), thereafter at 24 and 72 hours, 7 days and 14 days after first injection, and on day 1 of cycles 2 to 6.
- Tumor evaluation will be at baseline (within 14 days prior to randomization) and at the end of 3rd and 6th cycles of treatment (denoted as day 1 of cycle 4 and prior to surgery).

The randomization of 50 patients is expected to occur over approximately 24 months. The treatment and post-surgery evaluation will occur within 7 months. Thereafter patients will have no further follow-up. The end of the trial therefore will be approximately 31 months after randomization of the first patient.

The trial will be conducted in 7 Centers in Italy.

6. Patient selection

6.1. Criteria for patient eligibility

- 6.1.1. Female gender
- 6.1.2. Premenopausal status determined locally:
Estradiol (E2) must be above 54 pg/mL (or above 198 pmol/L), measured within 14 days prior to randomization.
- 6.1.3. Age \geq 18 years
- 6.1.4. Performance Status – Eastern Cooperative Oncology Group (ECOG) 0-1 (see chart at end of section*)
- 6.1.5. Histologically confirmed invasive breast cancer:
 - Primary tumor greater than 2 cm diameter, measured by clinical examination and mammography or echography (cT2-4b)
 - Any nodal stage
 - No evidence of metastasis (M0)
- 6.1.6. Primary tumor must have ER and PgR $>50\%$ of the cells
- 6.1.7. Primary tumor must be HER2 negative (by IHC and/or ISH)
- 6.1.8. Hematopoietic status:
 - Absolute neutrophil count $\geq 1.5 \times 10^9/L$
 - Platelet count $\geq 100 \times 10^9/L$
 - Hemoglobin ≥ 9 g/dL
- 6.1.9. Hepatic status:
 - Serum total bilirubin $\leq 1.5 \times$ upper limit of normal (ULN). In the case of known Gilbert's syndrome, a higher serum total bilirubin ($< 2 \times$ ULN) is allowed
 - AST and ALT $\leq 2.5 \times$ ULN
 - Alkaline phosphatase $\leq 2.5 \times$ ULN
- 6.1.10. Renal status: Creatinine $\leq 1.5 \times$ ULN
- 6.1.11. Negative serum pregnancy test, within 2-weeks (preferably 7 days) prior to randomization. Pregnancy test has to be repeated before treatment start if treatment does not start within 15 days of the previous test.
- 6.1.12. The patient must be willing to use effective non-hormonal contraception (barrier method – condoms, diaphragm – also in conjunction with spermicidal jelly, or total abstinence) after the pregnancy test and up to surgery. Oral, injectable, or implant hormonal contraceptives or medicated IUD are not allowed within 2 months prior to randomization and during the trial.
- 6.1.13. Prior fertility treatment is allowed but must have been stopped at least 12 months before randomization

- 6.1.14. The patient has completed the baseline patient-reported symptoms questionnaire
- 6.1.15. Written Informed Consent (IC) must be signed and dated by the patient and the Investigator prior to randomization
- 6.1.16. The patient has been informed of and agrees to data transfer and handling, in accordance with national data protection guidelines
- 6.1.17. The patient accepts blood samples to be taken according to the schedule in section 17.4 for the determination of the primary endpoint
- 6.1.18. The patient agrees to make tumor (diagnostic core biopsy and surgical specimen) available for submission for central pathology review and to conduct translational studies as part of this protocol

NOTE: Central Pathology Review on the primary tumor is mandatory for this trial, but patients will be evaluated for eligibility according to tumor characteristics as determined by the local Pathologist. Both the diagnostic breast core biopsy specimen and the final breast surgical specimen must be submitted for Central Pathology Review.

* ECOG Performance Status:

| | |
|-------------|--|
| PS 0 | Fully active, able to carry on all pre-disease performance without restriction |
| PS 1 | Restricted in physically strenuous activity but ambulatory and able to carry out work of a light or sedentary nature, e.g., light housework, office work |
| PS 2 | Ambulatory and capable of all self-care but unable to carry out any work activities. Up and about more than 50% of waking hours |
| PS 3 | Capable of only limited self care, confined to bed or chair more than 50% of waking hours |
| PS 4 | Completely disabled. Cannot carry on any self-care. Totally confined to bed or chair |

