| GnRH agonist ² (arm A) or GnRH antagonist ³ (arm B) | | x | x | x | x | x | x | | |
| Letrozole ⁴ | |continuously..... | | | | | | | |
| Laboratory tests | | | | | | | | | |
| Hematology ⁵ | x | | | | x | | | x | |
| Blood chemistry ⁶ | x | | | | x | | | x | |
| CEA and Ca 15.3 ⁷ | x | | | | x | | | x | |
| Estradiol ⁸ | x | x | x | x | x | x | x | x | |
| Tumor Evaluation | | | | | | | | | |
| Mammography ⁹ | x | | | | x | | | x | |
| Breast Ultrasound ⁹ | x | | | | x | | | x | |
| Chest x-ray ¹⁰ | x | | | | | | | | |
| Abdominal US or CT ¹¹ | √ | | | | | | | | |
| Bone scan ¹² | √ | | | | | | | | |
| Other tests | | | | | | | | | |
| ECG | √ | | | | | | | | |
| Echocardiography | √ | | | | | | | | |
| Pathology eval (local) | x | | | | | | | | x |
| Biological samples | | | | | | | | | |
| FFPE sample ¹³ | x | | | | | | | | x |
| Serum sample ¹⁴ | x | x ¹⁴ | x | x | x | x | x | | |

x = mandatory √ = if medically indicated

Legend for trial schedule:

1. Pregnancy test has to be repeated before treatment start, if treatment does not start within 15 days of the previous test.

Neoadjuvant treatment: 6 cycles of 28 days each

2. Triptorelin 3.75 mg i.m. on day 1 of every cycle
3. Degarelix, Firmagon[®]
 - Day 1 of cycle 1: 240 mg s.c. given as two subcutaneous injections of 120 mg
 - Day 1 of cycles 2-6: 80 mg s.c.
4. Letrozole 2.5 mg/day orally, continuously for 6 cycles

Laboratory tests

5. Hematology (Hemoglobin, platelet count, white blood cell count including differential (absolute neutrophil count)) must be done within 14 days prior to randomization, before the start of cycle 4 treatment and at the visit prior to surgery.
6. Blood chemistry (blood urea nitrogen, creatinine, alkaline phosphatase, AST and ALT, total bilirubin, calcium, urea, total cholesterol, LDL and HDL cholesterol, tryglycerides) must be done within 14 days prior to randomization, before the start of cycle 4 treatment and at the visit prior to surgery.
7. CEA and CA 15.3 must be done within 14 days prior to randomization, beginning of cycle 4 and at the visit prior to surgery.

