7.5. Stratification

For randomization, patients will be stratified by age (in years): less than or equal to 39 vs 40 or more.

Dynamic institution balancing will be used in order to balance randomized assignments within institutions.

8. Study drugs formulation and handling

Triptorelin, degarelix and letrozole are the investigational drugs used in this trial; all will be supplied.

Complete details of the study drug logistics, distribution, packaging, labeling and handling are described in a separate drug supply manual.

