9.1. Trial treatments

Six cycles of 28 days each:

Arm A: Triptorelin 3.75 mg i.m. on day 1 of every cycle + letrozole 2.5 mg/day orally for 6 cycles

Arm B: Degarelix 240 mg s.c. given as two subcutaneous injections of 120 mg on day 1 of cycle 1, followed by 80 mg s.c. on day 1 of cycles 2 to 6 + letrozole 2.5 mg/day orally for 6 cycles

Letrozole 2.5 mg/day orally should be started on day 1, concurrently with triptorelin or degarelix.

Trial treatment should start as soon as possible, and no later than 14 days after randomization.

NOTE: Treatment can be started at any time during the menstrual cycle.

Trial treatment stops at surgery.

If the patient has to continue endocrine treatment with an LHRH analogue after surgery, she should wait at least 6 weeks from the date of last administration of degarelix in order to avoid drug interactions.

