9.3. Timing of surgery

Definitive surgery should be performed within 2 to 3 weeks after the last administration of triptorelin or degarelix.

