13.5. Pregnancy

Pregnancies and suspected pregnancies of a patient occurring during trial treatment, or within 30 days of the last dose of trial drug(s), are considered immediately reportable events. Trial drug(s) are to be discontinued immediately and the patient instructed to return any unused portion of the trial drug(s) to the Investigator. The pregnancy, suspected pregnancy, or positive pregnancy test must be reported within 24 hours of the Investigator's knowledge using the Pregnancy Form (Form 41-PREG) to the IBCSG who will inform Ferring immediately.

The patient should be referred to an obstetrician-gynecologist, preferably one experienced in reproductive toxicity for further evaluation and counseling.

The Investigator will follow the patient until completion of the pregnancy, and must notify IBCSG immediately about the outcome of the pregnancy by completing the corresponding section on the Pregnancy Form (41-PREG).

All neonatal deaths that occur within 28 days of birth should be reported, without regard to causality, as SAEs. In addition, any infant death after 28 days that the Investigator suspects is related to the in utero exposure to trial drug(s) should also be reported within 24 hours of the Investigator's knowledge of the event using the SAE Forms.

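### Required contraception ends at surgery, 7 to 14 days before the SAP's injection exposure period is over and before the 30-day pregnancy window closes; one line of wording would align them

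*Protocol*

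**What the plan says.** Protocol 6.1.12, repeated in the eligibility part of the synopsis, asks the patient to use effective non-hormonal contraception (barrier methods or abstinence) "after the pregnancy test and up to surgery". No supplied section asks for contraception after surgery.

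Four other places fix the timing around it:

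- **Surgery.** Section 9.3: "Definitive surgery should be performed within 2 to 3 weeks after the last administration of triptorelin or degarelix".
- **Letrozole.** Section 8: "Triptorelin, degarelix and letrozole are the investigational drugs used in this trial". Note 4 to the trial schedule gives the dosing: "Letrozole 2.5 mg/day orally, continuously for 6 cycles". Section 9.1 adds: "Trial treatment stops at surgery".
- **Pregnancy.** Section 13.5 covers pregnancies during trial treatment "or within 30 days of the last dose of trial drug(s), are considered immediately reportable events". It goes on to require follow-up to the outcome and speaks of exposure of the fetus to trial drugs.
- **Exposure.** SAP 3.5.1.1 counts triptorelin or degarelix exposure to 28 days after the last injection, and letrozole exposure to one day after the last dose.

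**The concern.** The patients are premenopausal by criterion. The rule releases them from contraception at surgery, when the last depot injection is still inside its 28-day dosing interval and the SAP still counts them as exposed. A pregnancy conceived in the following days would have to be reported within 24 hours and followed to its outcome under 13.5, yet the criterion asks for no protection on those days. Fetal safety is at stake. The primary endpoint and its analysis are not touched.

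**Working it through.** There is no computed figure in the plan to reproduce. The check is a day count from the stated schedule.

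**Inputs.** Six cycles of 28 days with an injection on day 1 of each (9.1); surgery 14 to 21 days after the last injection (9.3); injection exposure to last injection + 28 days and letrozole exposure to last dose + 1 day (SAP 3.5.1.1); pregnancy window to 30 days after the last dose of trial drug(s) (13.5).

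**Step 1: can letrozole run to surgery?** The sixth injection falls 5 × 28 = 140 days after the first. Surgery falls at 140 + 14 = 154 to 140 + 21 = 161 days. Six full cycles would end at 6 × 28 = 168 days, so surgery comes 168 − 161 = 7 to 168 − 154 = 14 days before cycle 6 would finish. An on-schedule patient can therefore still be taking letrozole when she reaches surgery.

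**Step 2: the windows, in days after the last injection.**

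| | Surgery at day 14 | Surgery at day 21 |
|---|---|---|
| Required contraception ends | 14 | 21 |
| SAP injection exposure ends | 28 | 28 |
| 13.5 window closes, counted from the injection | 30 | 30 |
| 13.5 window closes, letrozole taken to surgery | 14 + 30 = 44 | 21 + 30 = 51 |
| Uncovered days inside SAP injection exposure | 28 − 14 = 14 | 28 − 21 = 7 |
| Uncovered days in 13.5 window, injection only | 30 − 14 = 16 | 30 − 21 = 9 |
| Uncovered days in 13.5 window, letrozole to surgery | 30 | 30 |

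If the last tablet is taken the day before surgery, the last row becomes 29 days.

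**Step 3: how much of the 30 days is exposure by the plan's own definition?** Letrozole exposure ends one day after the last dose, so it adds nothing beyond the injection period. The 30 days split into 14 + 16 (surgery at day 14) or 7 + 23 (surgery at day 21). Only 7 to 14 days lie inside an exposure period that the SAP defines; the other 16 to 23 belong to the reporting window alone.

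**Step 4: patients who stop early.** With surgery d days after the last dose of any trial drug, the gap to the 13.5 window is max(0, 30 − d). It shrinks as d grows and is 0 from d = 30 onward.

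**Step 5: the proposed rule.** Cover would end at the later of surgery and last dose + 30 days.

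- It is never earlier than surgery, so no patient loses cover.
- It is never earlier than last injection + 30 days, so it always passes the end of SAP injection exposure (day 28).
- With d = 40, a bare 30-day rule would end cover 10 days before surgery; taking the later date keeps it to day 40.

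**The case against.** The strongest reply is that 13.5 is a reporting rule. Its 30 days are also the general post-treatment window for adverse events (13.1) and serious adverse events (13.4.1). Such windows exist to catch late events, and nothing in the documents says contraception must match them. That stands: a reporting window may outlast a contraception requirement, so there is no contradiction.

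The 7 to 14 days inside injection exposure are also the days when conception is least likely. Section 9.2 stops treatment if suppression is not reached within 56 days by local limits, and local estradiol is measured at each cycle and before surgery (11.3.6, 11.5.5). A six-cycle patient should therefore be suppressed until about day 28. This largely stands, but it does not help a patient sent to surgery under 9.2 because suppression failed.

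Safeguards exist too: the visit 30 days after surgery collects adverse events, and 13.5 provides for rapid reporting and referral. These deal with a pregnancy once it is known; they do not prevent one.

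Three stronger readings are tempting, and the documents do not support them:

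- A reader might take the 30 days as 30 days of uncovered drug exposure. The SAP's letrozole definition rules that out.
- A reader might cite the 6-week wait in 9.1 as evidence of lasting degarelix exposure. That sentence concerns only a patient continuing on an LHRH analogue: "she should wait at least 6 weeks from the date of last administration of degarelix in order to avoid drug interactions". It says nothing about conception and should not be used here.
- A reader might infer that patients were told nothing about contraception after surgery. The patient information is not in the public copy, so longer advice there cannot be excluded.

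**Conclusion.** The point holds as a modest patient-safety improvement. For an on-schedule patient, required contraception stops 7 to 14 days before the SAP's injection exposure period ends. It stops 9 to 16 days before the 13.5 window closes if only the injection counts, and about 30 days before if letrozole is taken to surgery.

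These figures assume that surgery follows 9.3 and, for the largest one, that letrozole continues to the day of surgery. The pregnancy risk in the gap cannot be sized: the documents give no time to ovarian recovery, no washout time for conception and no expected number of pregnancies. Section 8.2 reports that degarelix has been given safely to women for infertility, which neither shows nor excludes a fetal risk in combination with letrozole. Aligning the two windows is a judgement, worth making because it costs little.

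**What to change.** In 6.1.12 and in the synopsis, replace the end point at surgery with: *until surgery or 30 days after the last dose of any trial drug (triptorelin, degarelix or letrozole), whichever is later*. The 30 days is borrowed from 13.5 so that the windows agree; it is not a claim about pharmacological washout. Then check that the patient information says the same.

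The cost is one sentence in two places plus that check. For the patient it means a few more weeks of barrier contraception or abstinence: about 30 days if letrozole runs to surgery, less if she stopped earlier, and none if surgery comes 30 days or more after her last dose. Sample size, power and analysis are unaffected. SAP 1.2 records enrolment as closed in January 2017, so the change would now serve mainly to correct the text for any reuse.
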